glycemic control.⁴²⁻⁴⁴ treatment programs for adults with T2D should also monitor for glucose trends during the program and adjust medication doses as needed to avoid hypoglycemia. Existing physical activity programs have not always included these important safeguards — in part, because they were not integrated into clinics.²⁴ The proposed K23 trial will include these screening and treatment monitoring safeguards.

12.1.4 Why should we deliver an intervention in clinical practices? There are several reasons why clinical care settings are a highly relevant way to deliver interventions to treat adults with T2D and sedentary behavior. Clinical practices have key implementation features of **capability, motivation, and opportunity**.^{45,46} Despite these features, primary care clinics do not deliver evidence-based counseling programs due to several concerns, such as: excessive staff and clinician burden, lack of reimbursement, and lack of training for clinicians/staff to deliver counseling.⁴⁷⁻⁴⁹ To integrate an activity intervention in clinics, we need to develop programs that address these barriers in a way that may be replicated in other systems.

[figure not shown]

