In addition to behavioral counseling targeting SCT constructs (Figure 4 in Significance), counselors will assist participants in the intervention group to set specific goals for physical activity in a paper log and on an electronic FitBit activity tracking device (see Appendix). Participants will record their actual physical activity next to their goals for easy review during counseling visits. Health promotion clinic staff will encourage participants to advance goals towards meeting U.S. physical activity guidelines of 150 minutes/week of moderate intensity activity (e.g., brisk walking) and 2-3 days/week of strength activities consisting of cycles of 5-10 repetitions of sit-to-stand, toe stand, chair dip, and side step-down (see Appendix).⁷⁵ Although achieving guidelines is a long-term physical activity goal, counselors will help patients to work towards this goal systematically but gradually. Participants and counselors will determine each person’s rate of physical activity increase to accommodate unique factors associated with their T2D, functional limitations, and fitness.

12.3g. USUAL CARE GROUP

Participants in the usual care arm will receive three mailings during the intervention phase (Table 7). Health promotion clinic staff will mail materials from the Center for Disease Control and Prevention website that address general healthy aging topics: i.e., advanced directive care planning, vision and hearing changes with aging, respectively. These mailings will be the only research contacts with participants during the 12-week intervention phase.

Table 8 Study visit activities, by study group

Visit	Phase	Intervention	Usual Care
1	Enrollment	Consent, baseline testing	Same as intervention arm
2-3	Baseline time (t) = 0 weeks	Baseline covariate and outcome testing	Same as intervention arm
4	t = 2 weeks	In-person clinic visit * with phone counseling†	None
5	t = 4 weeks	Phone counseling†	Print mailing on aging topic
6	t = 6 weeks	In-person clinic visit * with phone counseling†	None
7	t = 8 weeks	Phone counseling†	Print mailing on aging topic
8	t = 10 weeks	In-person clinic visit * with phone counseling†	None
9	t = 12 weeks	Phone counseling†	Print mailing on aging topic
10-11	Exit testing, t = 3 months	Exit covariate and outcome testing	Same as intervention arm

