Physical function	The Short Physical Performance Battery (SPPB) measures function with the following valid subscales: balance, usual walking speed, and repeated chair rise. The SPPB is sensitive to change for adults with moderate to severe functional impairment , and predicts disability and mortality. ^{68,89}	Ordinal, range 0-12	Aim 1 2° outcome
Lower extremity strength	Lower extremity strength will be measured as leg extensor (quadriceps) and leg flexor (hamstring) strength using [name] laboratory's established techniques. ^{38,90}	Continuous	Aim 1 Function predictor
Grip strength	Hand grip strength will be measured by dynamometer. ⁹¹	Continuous	Aim 1 2° outcome
Metabolic control outcome			
Hemoglobin A1c	Average glycemic control measured by standard methods ⁹²	Continuous	Aim 1
Covariates for adjustment			
Depression symptoms	Center for Epidemiologic Studies Depression Scale measures depressive affect severity and is valid in people with ^{93,94} and without T2D. ^{95,96}	Continuous	Aim 1 covariate for adjustment
Lower extremity arthritis pain symptoms	Western Ontario and McMaster Universities Arthritis Index—valid measure of knee and hip pain and stiffness. ⁹⁷	Continuous	Aim 1 covariate
Cognitive processing speed	Stroop test –measures cognitive processing speed as a valid predictor of cognitive function in adults with and without T2D. ⁹⁸⁻¹⁰⁰	Continuous	Aim 1 covariate

DEXA scan	DEXA will allow the calculation of body composition as fat-free mass and total mass so that we may report exercise performance levels standardized to these body composition measures.	Continuous	VO ₂ max covariate for adjustment
Cognitive executive function	Behavioral Dyscontrol Scale – valid measure of executive function in adults with and without T2D. ^{101,102}	Continuous	Aim 1 covariate
Process outcomes			
Acceptability	Percent of intervention patients who would recommend intervention ¹⁰³ ; Percent of clinical providers/staff who recommend continuing to offer the intervention to patients ¹⁰³	Percentile	Aim 2
Time burden	Patient time required for each intervention visit ¹⁰³ ; Staff/provider time required for each intervention visit ¹⁰³	Continuous	Aim 2
Safety outcomes			
	Participant report of outcomes after baseline testing: falls, musculoskeletal injuries, foot ulcers, hypoglycemia ^{20,24,57}	Continuous	Safety

12.3k. ANALYSIS OF ACCEPTABILITY OUTCOMES (Aim 2 and Safety analysis)

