Safety analysis: For ethical reasons, in addition to the acceptability outcomes addressed in Aim 2, we will monitor for study group differences in safety-related outcomes, in order to assess for any potential study harm. We selected the following safety outcomes based on relevant use in prior trials and per expert description of safety concerns in T2D; falls, musculoskeletal injuries, severe hypoglycemia (glucose <60 mg/dl or hospitalization/Emergency department visit for hypoglycemia).^{20,24,57} At study exit visit 9, we will ask participants if any of the following safety-related outcomes occurred since baseline testing was completed in visit 2: fall requiring clinical evaluation; fall that did not require clinical evaluation; musculoskeletal injury requiring clinical evaluation; musculoskeletal injury that did not require clinical evaluation; severe hypoglycemia (glucose <60 mg/dl or clinical evaluation for hypoglycemia), foot ulceration. For each safety outcome measured, we will descriptively report these as both dichotomous outcomes (Yes/No) as well as the frequency of safety events (e.g., number of hypoglycemic episodes). We will use ANCOVA to obtain preliminary data on the group differences in safety outcomes with adjustment for baseline conditions that may increase safety risk. Baseline conditions that may increase safety risk include the following: baseline moderate-to-severe impairment on SPPB (baseline score <10), prior history of fall, slowed cognitive processing speed).

12.3l POTENTIAL PROBLEMS AND ALTERNATIVE STRATEGIES We have planned alternatives for potential problems that may arise. For example, if participants report new medical concerns or symptoms during the telephone counseling sessions with the health promotion clinical staff, staff members will transfer the patient to the clinic triage nurse to evaluate the patient's symptoms. Also, if participants report new musculoskeletal pains to the health promotion clinic staff, the staff member will send an electronic health record note to the physician assistant conducting the in-person treatment visits to advise the patient on any recommended treatment or activity restrictions.

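### The hypoglycemia comparison in 12.3k may partly reflect unequal ascertainment between arms, and nothing is collected that would show how much

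*Combined protocol and SAP*

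**What the plan says.** Table 10 gives the source of the safety outcomes as "Participant report of outcomes after baseline testing: falls, musculoskeletal injuries, foot ulcers, hypoglycemia". Section 12.3k sets the time of collection: "At study exit visit 9, we will ask participants if any of the following safety-related outcomes occurred", looking back to baseline testing. The exit list contains "severe hypoglycemia (glucose <60 mg/dl or clinical evaluation for hypoglycemia), foot ulceration", where foot ulceration is a separate item. A few lines earlier the same section defines the outcome as "severe hypoglycemia (glucose <60 mg/dl or hospitalization/Emergency department visit for hypoglycemia", so the non-glucose limb is worded in two ways.

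Each safety outcome is to be reported as yes/no and as a number of events. ANCOVA is to give preliminary group differences, adjusted for three baseline conditions: SPPB below 10, an earlier fall, and slow cognitive processing.

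On contact, section 12.1.3 says that treatment programs should "monitor for glucose trends during the program and adjust medication doses as needed to avoid hypoglycemia", and adds: "The proposed K23 trial will include these screening and treatment monitoring safeguards". Section 12.3f has the physician assistant look for problems including hypoglycemia at the in-person visits. Table 8 places these at visits 4, 6 and 8 for the intervention arm and shows none for usual care. Section 12.3l sends participants who mention new symptoms in a counseling call to the triage nurse. For usual care, 12.3g describes three mailings and states: "These mailings will be the only research contacts with participants during the 12-week intervention phase".

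**The concern.** A participant can report a glucose value below 60 mg/dl only if somebody measured it. The other limb needs no self-check, but being clinically evaluated is more likely for someone who sees or speaks to clinic staff every two weeks. Both routes to a reported event appear more open in the intervention arm. None of the planned covariates bears on this.

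The comparison exists to detect harm from the intervention. If detection differs by arm, it could show an excess where true rates are equal, or hide a real reduction. The episode count is the more exposed of the two summaries, because recorded low values accumulate with the number of readings taken. As the plan stands, nobody could tell afterward which explanation applied.

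**Working it through.** **1. The plan's own figures.** The documents give no event rate, testing rate or power for hypoglycemia, so there is no figure to reproduce for this outcome. The only sample-size calculation (12.3j) is for physical activity: d = 0.61, two-sided alpha 0.05, 90 analysed, or 45 per arm. Power comes to 81.6% by t-test (82.5% by normal approximation), which agrees with the stated figure of over 80%. Attrition: 90 / (1 − 0.30) = 128.6, so 129, against 130 planned. Only the 45 per arm is used below.

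**2. Routes to a reported event, by arm.**
- Glucose limb: monitoring of trends is described as a safeguard of the treatment program (12.1.3). Nothing comparable is described for usual care.
- Clinical-evaluation limb: three in-person visits (12.3f, Table 8) and triage from calls (12.3l) in the intervention arm. Usual care has no study contact beyond mailings (12.3g).
- Common to both arms: the exit question only. No glucose log, testing record or symptom item is described for both arms.

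**3. Glucose limb alone.** Let r be the true risk of a value below 60 mg/dl and s the probability that such a value was measured. Then:

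observed risk = r × s

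observed ratio = (true ratio) × (s intervention / s usual care)

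The values of s and r are assumptions. Taking r = 10% in both arms:
- 60% vs 60% tested: 6% vs 6%, ratio 1.0
- 80% vs 60%: 8% vs 6%, ratio 1.33
- 60% vs 40%: 6% vs 4%, ratio 1.5
- 80% vs 40%: 8% vs 4%, ratio 2.0

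The ratio does not depend on r. In the other direction, a true ratio of 0.5 with 80% vs 40% detection gives 0.5 × 2.0 = 1.0, so a real halving would disappear.

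**4. Adding the clinical limb.** Let a share f of events be captured through clinical evaluation equally in both arms. With equal true risk:

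observed ratio = [f + (1 − f) × s intervention] / [f + (1 − f) × s usual care]

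- 80% vs 40%: f = 10% gives 0.82/0.46 = 1.78; f = 25% gives 0.85/0.55 = 1.55; f = 50% gives 0.90/0.70 = 1.29
- 80% vs 60%: f = 25% gives 0.85/0.70 = 1.21; f = 50% gives 0.90/0.80 = 1.13

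Equal capture is the favorable case. If intervention contacts generate evaluations, the dilution is smaller.

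**5. Scale in participants.** At 45 per arm, 8% vs 4% is 45 × 0.08 = 3.6 against 45 × 0.04 = 1.8 participants.

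**6. The covariates.** All three describe participants before randomization. A difference in detection that arises from contact after randomization is not removed by adjusting for them.

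**The case against.** The strongest reply is that unequal testing is inferred. The monitoring statement stands in the Significance section. No operational section specifies a glucose test, meter or schedule, and following trends could mean looking at readings that patients already take. Usual care is limited only in its research contacts. These are primary care patients with type 2 diabetes, and nothing says that their routine testing stops. All of this stands. A reader might infer that glucose is tested in the intervention arm only, or that the outcome mainly measures testing; the documents support neither.

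Nor is the event purely a laboratory value. The clinical-evaluation limb is part of the definition and dilutes the effect, as step 4 shows. It does not remove the problem, because that limb also depends partly on contact.

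The formula in step 3 further assumes that being tested is unrelated to having a low value. If symptoms prompt testing, the bias is smaller. The counts in step 5 are too small to support a firm reading of harm, and the plan itself calls the comparison preliminary. These points limit the size and importance of the concern, but they give no means of telling a detection artefact from a real difference.

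A reader might also infer from the visit number in 12.3k that usual care is never asked, since visit 9 in Table 8 is a mailing for that arm. Sections 12.3e and Table 8 place exit testing for both arms at visits 10-11, so the passages conflict and the text does not establish that the question is omitted.

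**Conclusion.** The concern holds in a limited form. Hypoglycemia is a single self-reported composite whose two limbs are both open to unequal ascertainment, and the planned contacts that could raise ascertainment are in the intervention arm. The between-arm comparison and the episode count may therefore partly reflect detection, and baseline adjustment cannot correct this.

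The size is unknown. For the glucose limb it runs from none (ratio 1.0, equal testing) to 2.0 at an assumed 80% vs 40%, and it is smaller for the composite. These figures rest on assumed testing shares, on testing being unrelated to low values, and, for the diluted figures, on equal capture of clinically evaluated events. The consequence is confined to interpreting a preliminary safety comparison. It is a cheap improvement to make before data collection and does not threaten the primary outcome.

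**What to change.** In 12.3k and on the exit form:
- Report the glucose limb and the clinical limb separately by arm, with all randomized participants who answered as the denominator.
- Add one exit question, worded identically in both arms, on how often glucose was checked. Report it descriptively beside the glucose limb. Do not use testers as the denominator and do not adjust for testing, because testing occurs after randomization and may be changed by the intervention.
- Take hospitalization or Emergency department visits as the main between-arm comparison, as the limb least dependent on study contact. The exit question as now worded does not single these out, so the form must record them separately.
- Do not interpret the pooled episode count as a group difference in harm.
- Reconcile the two wordings of the non-glucose limb within 12.3k.
- Reconcile the visit number given for the exit safety question with Table 8.

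The cost is one added question, a split of an existing item, and a few lines of analysis text. The drawback is that hospitalization or Emergency department events will be few, so that comparison will be imprecise.

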Summary: Taken together the preliminary data collected support the idea that an intervention in a clinical setting which allows for screening to identify appropriate patients and then implementing a clinic based intervention has the potential to improve physical activity and function in sedentary adults with T2D.

12.3i. OUTCOME MEASURES (see Table 10 on next page)

12.3j. POWER CALCULATION AND DATA ANALYSES FOR AIM 1 (EFFECTIVENESS)

Power Calculation: We used PASS version 11 to calculate power for the physical activity outcome.⁷⁸ Aim 1 was powered based on a previously observed effect size of Cohen's $d = .61$ when comparing a physical activity intervention to an education control group on physical activity of moderate-to-vigorous intensity⁷⁹ among older, obese adults. Assuming similar sized effects in the current study and a two-sided alpha of 0.05, the proposed sample size of $n=90$ will provide over 80% power to detect differences between the activity intervention and usual care for Hypothesis 1. If our effects match that of our preliminary data (increase in combined moderate-vigorous physical activity levels by 142 minutes/week across 3 participants (from 65 ± 80 to 207 ± 87 minutes/week, mean \pm SD), then we will have over 95% power to detect differences between the activity intervention and usual care. Enrollment of $n=130$ was planned to allow for up to 30% attrition. For Aim 1b, the proposed sample size will be sufficient to obtain stable means and standard deviations in order to calculate an accurate effect size estimate for physical function outcomes.

Data analysis: Before conducting the analyses by aim, we will assess descriptively and graphically the mean and distribution of each study outcome and covariate, in order to assess for outliers and skewed distributions. If variables are not normally distributed, we will consider logarithmic transformation.

Aim 1 Data Analysis

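### ANCOVA is the only model named for group differences in Yes/No and count safety outcomes, and its standard errors and intervals can mislead when events are absent, rare or strongly overdispersed (minor point)

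*Combined protocol and SAP*

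**What the plan says.** The safety analysis in section 12.3k gives its purpose: "we will monitor for study group differences in safety-related outcomes, in order to assess for any potential study harm". Six items are asked about at exit: falls and musculoskeletal injuries, each with or without clinical evaluation, severe hypoglycemia, and foot ulceration. On form, the plan says: "For each safety outcome measured, we will descriptively report these as both dichotomous outcomes (Yes/No) as well as the frequency of safety events". The next sentence names the model: "We will use ANCOVA to obtain preliminary data on the group differences in safety outcomes with adjustment for baseline conditions". The baseline conditions listed are "baseline moderate-to-severe impairment on SPPB (baseline score <10), prior history of fall, slowed cognitive processing speed".

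The safety row of Table 10 reads "Participant report of outcomes after baseline testing: falls, musculoskeletal injuries, foot ulcers, hypoglycemia" and gives the variable type as Continuous, although the same table uses other types elsewhere (the SPPB is Ordinal). The general data-analysis paragraph of section 12.3j plans a descriptive and graphical look at every outcome, and adds: "If variables are not normally distributed, we will consider logarithmic transformation".

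The documents name no logistic, Poisson, negative binomial, exact or score method, and give no rule for zero or sparse events. They also state no safety test, confidence interval, threshold or expected event rate.

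**The concern.** ANCOVA takes its standard error from a pooled residual variance, assumed equal in the two arms. For a Yes/No outcome the variance depends on the risk. For an event count with repeat events in a few participants, it rises faster than the mean. With about 90 analysed participants, three months of follow-up and six narrow items, some outcomes may have few events or none.

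The log transformation does not help. A transformed 0/1 variable still has two values, and the log of a zero count is undefined.

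The purpose is to look for harm, so the error that matters most is an upper limit for the excess in the intervention arm that is too low, because it reassures wrongly. Sparse tables can also err the other way, with an interval that excludes zero too readily.

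**Working it through.** **Inputs.** Section 12.3j plans n=90 analysed, which is 45 per arm at 1:1, and 130 enrolled, which is 65 per arm. Its own power figure reproduces: 45 per arm, d = 0.61 and two-sided alpha 0.05 give 81.6% (t) or 82.5% (normal), against the stated figure of over 80%; 90/0.7 = 129, against 130. There is no stated safety figure to reproduce. All event rates, count means and dispersions below are assumptions.

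**Formulas.** Two-group least squares, n per arm: d = p1 − p2; s² = [n·p1(1−p1) + n·p2(1−p2)]/(2n−2); SE = √(2s²/n); limits d ± t·SE, with t = 1.987 on 88 df. Newcombe: combine the two Wilson intervals (l1, u1) and (l2, u2); lower = d − √[(p1−l1)² + (u2−p2)²], upper = d + √[(u1−p1)² + (p2−l2)²].

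**No events, 0/45 v 0/45.** s² = 0, so the least-squares interval is 0 to 0. The Wilson upper limit for 0/45 is 7.9%, so Newcombe gives ±7.9 points. The exact two-sided upper limit per arm is 1 − 0.025^(1/45) = 7.9%. At 3% v 1% this table has probability 0.97^45 × 0.99^45 = 16.2%. It accounts for all of the drop in coverage to 81.8%; given at least one event, coverage is 97.6%.

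**A sparse table, 4/45 v 0/45.** d = 8.9 points; s² = 45 × 0.0889 × 0.9111/88 = 0.0414; SE = √(2 × 0.0414/45) = 0.0429; limits +0.4 to +17.4 points. Newcombe gives −0.6 to +20.7. Least squares excludes zero (p = 0.041), Newcombe does not, and Fisher's exact p is 0.117.

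**Yes/No outcomes, full binomial enumeration, given at least one event.**

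| Per arm | Intervention v usual care | Least squares: coverage, upper limit too low | Newcombe: coverage, upper limit too low |
|---|---|---|---|
| 45 | 4% v 2% | 95.7%, 3.9% | 99.4%, 0.2% |
| 45 | 6% v 3% | 93.0%, 5.5% | 98.4%, 1.2% |
| 45 | 8% v 4% | 95.6%, 3.1% | 97.6%, 1.1% |
| 45 | 10% v 5% | 95.0%, 3.4% | 97.1%, 1.8% |
| 45 | 10% v 1% | 93.7%, 5.5% | 98.5%, 0.7% |
| 65 | 3% v 1% | 92.1%, 7.1% | 99.4%, 0.4% |
| 65 | 4% v 2% | 93.1%, 5.5% | 98.3%, 1.2% |

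At 20% v 10%, 45 per arm, least-squares coverage is 94.9%. At equal risks of 1%, 2% and 5% it is 99.8%, 98.8% and 95.0%. Adjusting for three baseline terms changes little: in 10,000 simulated trials, 6% v 3% gave 93.4% coverage with 5.5% of upper limits too low. Firth logistic regression with profile-likelihood limits, on the odds-ratio scale, gave 97.1% and 2.6%.

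**Counts, 45 per arm, negative binomial, given at least one event: least-squares upper limit too low (nominal 2.5%).**

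| Means | k = 0.2 | k = 1 |
|---|---|---|
| 0.06 v 0.02 | 5.6% | not run |
| 0.10 v 0.02 | 10.0% | not run |
| 0.15 v 0.05 | 8.0% | 5.3% |
| 0.30 v 0.10 | 8.0% | 4.5% |
| 0.6 v 0.3 | 6.2% | 3.6% |

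At equal means of 0.1 and 0.3 with k = 0.2, least-squares coverage is 95.6% in both cases.

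**The case against.** The strongest reply is that these errors belong to an output the plan never promises. No safety interval or test is stated, the model is only for preliminary data, and events are also tabulated. That stands, and it is why the point is minor. An estimated group difference still needs a usable measure of uncertainty, and the plan offers no other source for one.

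Second, a reader might infer that the plan fits ANCOVA to the Yes/No form. The documents do not say so. The Yes/No form appears in the sentence on descriptive reporting, and the ANCOVA sentence speaks only of safety outcomes. If the model is meant for frequencies alone, the count results above are the relevant ones. Either way, the plan should say which.

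Third, with no events at all, the planned tabulation shows zero in each arm, so few readers would take 0 to 0 at face value. That is fair, but the table alone does not show what risk remains compatible with the data.

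Fourth, the Yes/No shortfall is modest and moves up and down with the assumed rates. Newcombe is conservative, so it flags a true excess less often. Both statements are correct, and the choice is a trade-off.

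Fifth, the graphical check in section 12.3j would reveal sparse data. It would, but the only remedy offered there is the log transformation.

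**Conclusion.** The point holds as a minor one. ANCOVA is the only model named, the Table 10 type conflicts with the form described in section 12.3k, and nothing else in the plan supplies a suitable method. Intervals from the model can mislead with no events, in some rare-event settings with a true excess (5.5% to 7.1% of upper limits too low in the worst cases enumerated), and for strongly overdispersed counts (about 8-10% at means from 0.10 v 0.02 to 0.30 v 0.10, k = 0.2).

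A reader might infer that the safety comparison is biased or that false alarms are inflated. Neither follows. With randomised arms the estimated difference is unbiased, coverage at equal risks was at or above nominal, and commoner Yes/No outcomes are close to nominal. No primary result, sample size or stopping rule depends on this analysis.

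The size rests on assumed rates and dispersions, because the documents give none. The text and the zero-event result need no such assumption.

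**What to change.** Replace ANCOVA for the safety outcomes:

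- **Yes/No (main comparison).** For each outcome, give participants with at least one event as n (%) per arm, and the risk difference with a Newcombe or Miettinen-Nurminen 95% CI. With no events in either arm, add the exact per-arm upper limit for the proportion of participants (0/45: 7.9%).
- **Adjustment (supporting).** Firth logistic regression on treatment and the three listed baseline conditions, with the number of events shown beside it.
- **Counts.** Report events and rates per arm descriptively. Give a negative binomial rate ratio with likelihood-ratio limits only when both arms have events and the model converges. Do not use exact conditional Poisson limits when an arm is empty, because repeat events in one participant break their assumption. For example, one participant with 6 events against an empty arm gives a lower limit for the proportion of 0.025^(1/6) = 0.541, hence a rate ratio of 0.541/0.459 = 1.18, which excludes 1 on the strength of one person.
- **Table 10.** Retype the safety row as binary/count.

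The cost is SAP wording and minor programming. Rare-event intervals become wider and exclude zero less often: 34.9% v 51.6% of trials at an assumed 10% v 1%, and 4.8% v 12.6% at 5% v 1%. The adjusted result moves to the odds-ratio scale and says little when events are few. For commoner counts the negative binomial model is not always better: at equal means of 0.3 (k = 0.2) its coverage was 93.2% in trials with events in both arms, against 95.6% for least squares in trials with any event.
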